The goal of this study is to investigate the risk of COPD exacerbations, community acquired pneumonia, and health care utilization in patients treated with Tio+Olo in comparison to patients treated with ICS/LABA/LAMA. All analyses will be conducted for the total population, as well as in sub-groups of patients under (1) high- or low risk of exacerbation based on previous history of exacerbations in the year preceding cohort entry (cut-off: 0-1 vs 2+ exacerbations [P07-11503], (2) circulating eosinophils (cut-off B-Eos 300 cells/uL, [P18-09975]), and (3) as an exploratory analysis, a combination of exacerbation history and circulating eosinophils.

Primary objectives:

The primary objective is to compare the effectiveness of new use of maintenance therapy initiation with the combination treatment Tiotropium and Olodaterol (Tio+Olo) compared with new use of LABA/LAMA/ICS combination in COPD as the time to the first COPD exacerbation.

Secondary objective:

The secondary objective is to assess the association between maintenance therapy initiation with the combination treatment (Tio+Olo vs any LABA/LAMA/ICS combination in COPD and time to community acquired pneumonia.

Exploratory objective:

To assess differences between Tio+Olo vs any LABA/LAMA/ICS in all-cause and COPD-specific healthcare utilization and cost overall and by care setting.

Proprietary confidential information © 2019 Boehringer Ingelheim International GmbH or one or more of its affiliated companies

7. **RESEARCH METHODS**

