7.3 SUBJECTS

The study cohort will be formed based on the following entry criteria.

Inclusion Criteria:

- 1. At least one prescription for Tio+Olo or a LABA/LAMA/ICS combination between 1 January 2013 and 31 March 2019.
 - a. For Tio+Olo users, the first dispensing of Tio+Olo will be defined as the index date.
 - b. LABA/LAMA/ICS use can occur either in free or fixed combinations. The first date when all three medications are used based on either concurrent or overlapping dispensings in the pharmacy claims data will be defined as the index date.
- 2. At least one diagnosis of COPD at any time prior to the index date.
- 3. At least one year of continuous medical and pharmacy health plan eligibility prior to the index date will be required to allow a baseline period for the covariates and identification of new use of the study drugs.

Exclusion Criteria:

- 1. To increase the likelihood of a true diagnosis of COPD, we will exclude:
 - a. All patients less than 40 years of age on the index date, and
 - b. All patients with a diagnosis of asthma in the year prior to the index date
- 2. To limit the population to those without severe lung compromise outside of COPD, we will exclude individuals with lung cancer, interstitial lung disease, or lung transplant identified at any time prior to the index date
- 3. To restrict the cohort to new users of Tio+Olo or LABA/ICS, we will exclude any individual with use of either Tio+Olo, LABA/ICS, or LABA/LAMA/ICS combination therapy in free or fixed form for at least one year prior to the index date.

Outpatient laboratory data is available for a subset of patients. Some analyses will be further restricted to the subset of the population with at least one laboratory result showing circulating eosinophil levels within six months before the index date.

Individuals in the study cohort will be followed from the index date until the earliest of the date of a switch in treatment, addition of ICS for the Tio+Olo group, discontinuation of

COPD treatment, the end of the study period, or the end of continuous health plan eligibility. Main analyses will be further limited to the first year after cohort entry, with sensitivity analyses considering all available data.

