7.4 VARIABLES

7.4.1 **Exposures**

The exposure measures are based on pharmacy dispensings of the study medications, namely Tio+Olo and LABA/LAMA/ICS combination therapy. As described in the data analysis section, the as-treated analysis, which is the main analysis, will consider continuing exposure of the initial treatment of Tio+Olo or LABA/LAMA/ICS within the treated groups defined by the days supply recorded at the time of pharmacy dispensing, allowing for a gap between dispensings of up to 15 days. This gap is allowed in consideration of plausible delays in obtaining medication refills and continued use beyond the days supplied where medication has been missed due to imperfect adherence, and will be varied in sensitivity analyses (see Section 7.9.2). Codes used to identify study medications are included in Annex 3.1.

The treatment segment ends at the earliest of the following events:

- 1. Fifteen days after the end of the observed days supply for the medication received on the index date without a subsequent dispensing of COPD medication (i.e., discontinuation)
- 2. Initiation of triple therapy (i.e., addition of ICS to Tio+Olo or a LAMA to LABA/ICS (i.e., treatment escalation, applies to Tio+Olo only)
- 3. Any other change in use of study medication by active ingredient, inclusive of a change to a different combination therapy, change from a fixed form to a free form combination therapy, or a change from combination therapy to monotherapy (i.e., switch)

Changes in dose for medications started on the index date will not impact the end of the treatment segment. Codes used to identify study medications are included in Annex 3.1.

7.4.2 **Outcome(s)**

7.4.2.1 **Primary outcome(S)**

The primary outcome event for effectiveness is the first COPD exacerbation to occur after cohort entry. The event is defined as follows:

- Severe exacerbation: •
 - Hospitalization with a principal discharge diagnosis of COPD.
 - Moderate exacerbation:
 - An ED visit with a discharge diagnosis of COPD and/or
 - Dispensing of an antibiotic and an oral corticosteroid on the same day

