7.9 DATA ANALYSIS

7.9.1 Main analysis

All analyses will be presented for each group (Tio+Olo vs LABA/LAMA/ICS) overall and stratified as follows:

- History of exacerbation: 0 inpatient and 0-1 outpatient events
- History of exacerbation: 1 + inpatient or 2 + outpatient events
- Circulating eosinophils: B-Eos < 300 ug/mL
- Circulating eosinophils: B-Eos 300 ug/mL+
- History of exacerbation: 0 inpatient and 0-1 outpatient events & circulating eosinophils: B-Eos < 300 ug/mL
- History of exacerbation: 0 inpatient and 0-1 outpatient events & circulating eosinophils: B-Eos 300 ug/mL +

We will first describe formation of the study cohort. Patient characteristics at baseline in patients treated with Tio+Olo and patients treated with LABA/LAMA/ICS will be described using standard descriptive statistics. Because eosinophil levels may vary based on exacerbation, we will also provide a count and percentage of the number of individuals whose eosinophil results were recorded within 30 days of an exacerbation event.

High-dimensional propensity scores including both pre-specified and data-derived variables will then be calculated. We will use fine stratification and reweighting of the exposure propensity score to control for measured covariates [R19-3030]. Balance of patient characteristics between the cohorts will be described before and after propensity score application and compared using standardized differences (in the crude population and the reweighted pseudo-population). Standardized differences greater than 0.10 (10%) will be taken to indicate imbalance and further refinement approaches will be applied.

For the analysis of the primary objective, a Cox proportional hazard regression model will be used to perform an as-treated analysis that assesses the effect of current use of LABA-LAMA-ICS combination versus the Tio+Olo combination on the risk of a first COPD exacerbation. It will provide an estimate of the hazard ratio (HR) of a COPD exacerbation associated with LABA-LAMA-ICS use relative to Tio+Olo use, along with 95% confidence intervals (CI).Current use will be defined based on the days supply during the period of overlap, allowing a grace period of 15 days following the end of days supply to account for intermittent use. This approach allows consideration of exposure as time-dependent, accounting for the changes in exposure during the follow-up. In particular, this analysis excludes patients stopping one or more of the drugs prior to the index date.

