Stratified analyses will use the same approach. Because not all individuals will have available laboratory result data available, fine stratification and reweighting by propensity score will be repeated within the subset of the cohort with available results to create weighted populations suitable for these stratified analyses. Potential effect-modification by B-Eosinophils and/or exacerbation history will be studied by comparing models with and without interaction terms and through qualitative consideration of differences in stratum-specific estimates.

The analysis of the risk of pneumonia will also use a time-dependent Cox proportional hazard regression model with an as-treated approach, similar to that of the primary analysis.

In addition, we will repeat the primary effectiveness analysis on the time to exacerbation separately for moderate and severe exacerbations.

In terms of healthcare utilization, we will present continuous and categorical variables using standard descriptive statistics to describe total visits and total costs related to inpatient, outpatient, office visit, and emergency care as well as total pharmacy dispensings, distinct medications used, and pharmacy costs. Utilization and costs will be stratified to facilitate comparison between Tio+Olo and LABA/ICS, and presented by individual setting and as a composite. All-cause and COPD-specific data will be shown.

Proprietary confidential information © 2019 Boehringer Ingelheim International GmbH or one or more of its affiliated companies

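### Utilization and cost are to be compared between arms as descriptive totals, with no stated observation window, person-time scale or link to the propensity weights

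*Combined protocol and SAP*

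**What the plan says.** Section 6 sets a comparative exploratory objective: "To assess differences between Tio+Olo vs any LABA/LAMA/ICS in all-cause and COPD-specific healthcare utilization and cost overall and by care setting". Section 5 names payers among the intended readers.

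The method is one paragraph near the end of section 7.9.1. It uses descriptive statistics only, to "describe total visits and total costs related to inpatient, outpatient, office visit, and emergency care as well as total pharmacy dispensings", followed by distinct medications and pharmacy costs. The paragraph continues: "Utilization and costs will be stratified to facilitate comparison between Tio+Olo and LABA/ICS". It names no window, denominator, weights, model or interval.

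The follow-up rule is in section 7.3 and covers the whole cohort: "Individuals in the study cohort will be followed from the index date until the earliest of the date of a switch in treatment", with further exits at ICS addition for Tio+Olo, discontinuation, end of study and end of plan eligibility. Main analyses stop at one year. Section 7.4.1 marks one exit as arm-specific: "treatment escalation, applies to Tio+Olo only". It also ends a segment at any other change of active ingredient or a move from a fixed to a free combination.

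On confounding, section 7.9.1 says in general terms: "We will use fine stratification and reweighting of the exposure propensity score to control for measured covariates".

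**The concern.** A total accumulated over a variable period measures rate multiplied by time. If one arm stays on its regimen longer, its patients accumulate more visits, dispensings and cost at the same monthly rate. The arm that leaves treatment sooner looks cheaper for that reason alone.

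The exit rules give no ground for assuming equal time. ICS addition ends follow-up for Tio+Olo only. Triple therapy may be fixed or free, and section 7.9.1 bases current use on the overlap of days supply, so a lapse or change in one of several inhalers can end the triple segment.

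The second issue is confounding. Sections 7.6 and 7.11 both accept that confounding by indication could be a problem. If the utilization tables use the crude cohort, they carry whatever baseline difference exists between dual and triple users. An artefactual cost difference would go straight to a payer audience.

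**Working it through.** **Plan's own figure.** The documents give no effect size, precision or follow-up figure for utilization or cost, so there is nothing to reproduce.

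**Step 1: is the window or the weighting fixed elsewhere in 7.9.1?** Other analyses there are tied to an approach. The subgroup analyses use the same approach as the main one. Pneumonia is described as similar to the primary analysis. The moderate and severe analyses repeat the primary effectiveness analysis. The utilization paragraph has no such link. Section 7.9.1 creates both a crude and a reweighted population, and the paragraph does not say which is used. No separate window is defined, so the natural reading is the as-treated follow-up of section 7.3.

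**Step 2: effect of unequal follow-up on totals.** Take the per-patient total over follow-up. With the same monthly rate r in both arms,

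ratio of mean totals = (r × T1) / (r × T2) = T1 / T2.

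Mean follow-up by arm is not in the documents, so these values are assumed:

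- 180 vs 150 days: 180/150 = 1.20, a 20% difference.
- 200 vs 150 days: 200/150 = 1.33, a 33% difference.

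A second illustration uses exponential persistence with mean m months, capped at 12 months, so mean follow-up is m × (1 − exp(−12/m)):

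| Assumed m, Tio+Olo / triple | Mean follow-up (months) | Ratio of totals, triple / Tio+Olo |
|---|---|---|
| 6 / 6 | 5.19 / 5.19 | 1.00 |
| 6 / 5 | 5.19 / 4.55 | 0.88 |
| 6 / 4 | 5.19 / 3.80 | 0.73 |
| 6 / 3 | 5.19 / 2.95 | 0.57 |
| 4 / 6 | 3.80 / 5.19 | 1.37 |

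The rate ratio per person-month is 1.00 in every row.

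**Step 3: how much confounding is visible?** Inputs are the preliminary counts in section 7.7, which show no step for the asthma or other lung-disease exclusions.

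- High exacerbation history, Tio+Olo: 226 + 105 + 537 = 868; 868/5,469 = 15.9%.
- High exacerbation history, triple: 1,888 + 707 + 4,822 = 7,417; 7,417/42,227 = 17.6%.
- Standardized difference = (0.1756 − 0.1587) / √[(0.1587 × 0.8413 + 0.1756 × 0.8244)/2] = 0.045, against the plan's threshold of 0.10.
- Eosinophils of 300 cells/µL or more, among those with a result in the stratified rows: 586/2,193 = 26.7% vs 4,188/15,592 = 26.9%; standardized difference 0.003.

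If a high-history patient costs R times as much as a low-history patient (assumed), imbalance in this marker alone shifts the cost ratio by (1 + 0.1756(R − 1)) / (1 + 0.1587(R − 1)). That is 1.015 for R = 2 and 1.041 for R = 5, or about 1.5% to 4.1%.

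**Step 4: comparator.** The opening of section 7.9.1 sets the arms for all analyses as Tio+Olo and LABA/LAMA/ICS. The utilization paragraph names LABA/ICS, which is not an arm of this study.

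**The case against.** The strongest reply is that the plan is silent rather than wrong. The abstract presents propensity-score reweighting as the study's confounding control, and the sentence in section 7.9.1 is not restricted to the Cox models. A reader might infer that the tables are explicitly unadjusted. The documents do not say so, and that reading does not stand.

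A reader might also infer that follow-up is known to differ between arms. It is not. No persistence figure is given, the exit rules push in opposite directions, and equal means are possible.

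Nor do the tabulated markers show strong channelling. Both lie well below the 0.10 threshold, and section 7.9.1 already presents all analyses by exacerbation history. Other confounders are not tabulated, so this neither shows nor excludes a larger imbalance.

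The objective is exploratory and no test or interval is promised, which lowers the weight of the point. The LABA/ICS label also appears in sections 7.3 and 7.4.2.1 and is a separate drafting slip. Finally, the table of contents lists an Annex 3.4 on statistical considerations whose text is not in the material available here. If it settles the window, scale and weighting, the point falls to that extent.

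What survives is that the stated objective is a between-arm difference, the stated metric is a total, and the only stated follow-up is variable as-treated time.

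**Conclusion.** The concern holds in limited form. As written, a between-arm difference in utilization or cost could not be interpreted, because it cannot be separated from time on treatment or from any confounding left if the tables are unweighted. The documents do not support saying that the differences will reflect time and channelling rather than treatment.

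Unequal time is the main argument. Under the assumed scenarios the ratio of totals runs from 0.57 to 1.37 with no true difference, and the direction is unknown. Measured channelling on exacerbation history would add only about 1.5% to 4.1% under the assumed cost ratios. The conclusion rests on reading the section 7.3 follow-up as the window for these outcomes. A fixed window for all patients would change the problem. Because the objective is exploratory, this should be corrected but does not threaten the primary analysis.

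**What to change.** In section 7.9.1:

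1. State the observation window for utilization and cost, and report follow-up time by arm.
2. Replace totals with visits, dispensings and costs per person-month of first-year on-treatment follow-up in the fine-stratification-weighted population. Give robust or bootstrap 95% confidence intervals, by care setting, all-cause and COPD-specific, with crude values alongside.
3. Correct the comparator from LABA/ICS to LABA/LAMA/ICS.
4. State as a limitation that scaling by person-time does not fully remove informative censoring, for example when costs cluster around the index date or a treatment change.

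A 12-month-from-index analysis regardless of treatment change is optional. If restricted to patients with 12 months of enrolment, it should be labelled as conditioning on retained enrolment, which brings its own selection.

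The cost is revised wording and modest extra programming. The weights and person-time are already needed for the Cox models.

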7.10 QUALITY CONTROL

HealthCore operates observational research studies with the goal that the services provided to our clients are of high quality. To support this imperative we believe it is critical 1) to have dedicated training and quality resources and 2) that all talking points and major processes to be implemented with the study be approved by Boehringer Ingelheim in advance.

HealthCore's quality control program is centralized within the Regulatory Compliance Office. The Regulatory Compliance Office Manager is responsible for quality control and reports directly to the Vice President of Operations of HealthCore on all quality matters. HealthCore's quality system is organized around the Quality Manual, the quality checks within the project life cycle, and Standard Operating Procedures (SOPs). HealthCore has procedures for retention of protected health information (PHI) and project data. The study will be tracked at various levels to help ensure that all aspects including project delivery, infrastructure, quality processes, resource management, and financial issues are addressed. To help ensure the highest level of quality on every project, HealthCore has established several layers of quality assurance throughout the project lifecycle.

Role Based Control Checks: Each member of the team is responsible to perform thorough quality control checks on their work. In addition, the PI and Research Project Manager are also accountable for quality of all deliverables.

Quality Check Points: Centralized "checkpoints" have been implemented during the data management cycle to help ensure accurate translation of programming requests.

Quality Assurance Standards: Standard review procedures have been developed and are applied throughout the project lifecycle.

Automation: HealthCore has developed standard definitions of many variables and disease states and developed programs to apply these standards as needed on projects. These standards help ensure consistency, repeatability and accuracy for each project.

7.11 LIMITATIONS OF THE RESEARCH METHODS

Several potential biases are inherent to any observational study in the HIRD. In the absence of randomization, confounding by indication could be an issue. Controlling for propensity to add the second treatment should limit this bias, but can control only for measured covariates and may produce estimates that are impacted by residual confounding. This is of particular importance in the case of lifestyle factors that are less critical to insurance billing and thus poorly captured in claims data. Quantitative bias analyses can formally describe the extent to which these issues are present, but bias analysis parameters are informed by literature and clinical expert opinion. As such, the accuracy of bias corrected analyses is limited by the accuracy of the assumptions that inform them.

Second, there is the possibility of information bias due to misclassification of the outcomes or exposure or missing data, especially, differential missingness of some data (e.g. eosinophils, which may only be measured in sicker patients). The prescriptions dispensed by a pharmacy but not taken by patients could lead to misclassification of exposure. Pharmacy dispensing data does bring us one step closer to patient use than physician prescribing given that the patient has taken the effort to obtain the medication as instructed, however, information such as indication can only be inferred based on diagnostic patterns.

7.12 OTHER ASPECTS

None

 Study Number 1237-0094
 c30699487-01

 Proprietary confidential information © 2019 Boehringer Ingelheim International GmbH or one or more of its affiliated companies

8. PROTECTION OF HUMAN SUBJECTS

HealthCore maintains Data Sharing Agreements (DSAs) and Business Associate Agreements with covered entities that provide protected health information (PHI) incorporated into the HealthCore Integrated Research Database (HIRD). HealthCore's access, use, and disclosure of PHI are in compliance with the Health Insurance Portability and Accountability Act (HIPAA) Privacy Rule [45 CFR Part 160 and Subparts A and E of Part 164]. HealthCore does not access, use, or disclose PHI other than as permitted by HIPAA and its Business Associate Agreements. When using PHI for research, this typically means we will use PHI to create limited data sets for research, or when that is not feasible we may obtain a specific waiver of the HIPAA authorization requirements from an Institutional Review Board (IRB). HealthCore also takes into consideration other federal and state laws and regulations that might limit use of certain types of data more than HIPAA, including those laws related to identifiable records related to substance abuse and human immunodeficiency virus.

The current study is designed as an analysis based on medical and pharmacy claims data from a large insured population in the United States (US). There is no active enrollment or active follow-up of study subjects, and no data will be collected directly from individuals.

At no time during the conduct of this study will HealthCore provide patient or provider identifying information to Boehringer Ingelheim All data and/or results will be in an aggregated and de-identified format. Data variables with values ≤ 10 will be reported only as " ≤ 10 ." Boehringer Ingelheim will not attempt to re-identify any results provided for the study.

Proprietary confidential information © 2019 Boehringer Ingelheim International GmbH or one or more of its affiliated companies

